 1. Spatial Working Memory (SWM): measures spatial memory functions and takes about 10 minutes. It requires that subjects attend to and retain the location of several dots presented simultaneously on a computer display. They are requested to press buttons on a keyboard that correspond to whether a probe dot appeared in one of the same locations as the previous dots.

2. List Sort Working Memory: (10 minutes) This task is from the NIH Toolbox and assesses working memory and requires the participant to recall and sequence different visually and orally presented stimuli. Pictures of different foods and animals are displayed with both an accompanying audio recording and written text that names the item. The participant is asked to repeat the items back to the examiner in size ordered from smallest to largest.
- *Executive Function:*
 1. Trail Making B (5 min): This task measures executive control (part B). Both parts of this test consist of 25 circles distributed over a sheet of paper. In Part A, the circles are numbered 1-25, and the subject is instructed to draw lines to connect the numbers in ascending order. In Part B, the circles include both numbers (1-13) and letters (A-L); as in Part A, the patient draws lines to connect the circles in an ascending pattern, but with the added task of alternating between the numbers and letters (i.e., 1-A-2-B-3-C, etc.). The task is discontinued if the subject has not completed both parts after five minutes have elapsed.
 2. Dimensional Card Sort: (6 minutes) This task is part of the NIH Toolbox and measures cognitive flexibility and attention. Two target pictures are presented that vary along two dimensions (e.g. shape and color). Participants are asked to match a series of bivalent test pictures (e.g., yellow balls and blue trucks) to the target pictures, first according to one dimension (e.g., color) and then, after a number of trials, according to the other dimension (e.g., shape). The relevant dimension for sorting is indicated by a cue word (e.g., “shape” or “color”) that appears on the screen for all participants.
 3. Flanker: (4 minutes) This is a measure of inhibitory control and attention and is part of the NIH Toolbox. The task requires the participant to focus on a particular stimulus while inhibiting attention to the flanking stimuli.

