1.11 ANALYSIS PLAN

Our analysis plan has proposed an intent-to-treat analysis where all participants, regardless of whether they complete all sessions, will be invited to return for follow-up assessments. However, there will likely be some participants that refuse to return for follow-up assessments. “Lost to follow up” will be defined here as missing data that is contributing to the primary outcomes (executive functioning and hippocampal volume). The reason will be recorded (i.e., missed visit due to traveling, illness). These criteria and documentation will also be applied for any discontinued subjects with the reasons for discontinuation being recorded (i.e., moving out of state).

We propose to use all available data in the planned analysis for testing our primary outcomes. We will assess the missingness of data consistent with the assumptions of the modeling approach described above. That is, we will examine the randomness of missing data and examine if the data is missing completely at random (MCAR) or missing at random (MAR). Parameters of the GLMM will be estimated using the maximum likelihood estimation or restricted maximum likelihood methods that are known to produce consistent and efficient estimates under MAR.

Imaging data analysis. We will first analyze each imaging outcome (e.g., volume) separately from every other imaging outcome (e.g., fMRI). But, once voxel-wise associations related to the intervention are established, we could test, using hierarchical regression, the relative significance of each imaging measure to explain improvements in cognitive function with the intervention.

1.12 PARTICIPANT SAFETY:

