Power and Statistical Analysis: We will analyze in an intent-to-treat (ITT) manner such that all participants, regardless of whether they complete the intervention, will be invited to return for the follow-up sessions and will be included in primary analyses. Secondary analyses will be conducted using a per-protocol approach, which restricts the analysis to the participants that completed the intervention. All cognitive and neuroimaging data will be interrogated for normality and any non-normal data will be transformed. Any data that cannot be transformed will be analyzed using non-parametric tests. Non-parametric regression models will be used for continuous variables when necessary. Outlier de-weighting will be conducted to remove the influence of anomalous data. All analyses will be two-tailed. We will first summarize baseline demographic and brain characteristics of the sample and intervention groups by conducting Pearson, Spearman, and Chi-square statistics as appropriate. Our primary goals are to examine whether the intervention improves cognitive and brain health. To test these hypotheses, we propose to use a General Linear Mixed Model (GLMM) in standard neuroimaging and statistical packages. Effects of Time (baseline, 6-month), Group (Dance, Education), and Time by Group interactions will be examined. Post-hoc comparisons using least square means will decompose any significant interactions and will be plotted to illustrate the direction of the effect. Mean differences between groups for all cognitive and neuroimaging outcome measures will be derived using linear contrasts and multiple comparisons will be corrected by standard protocols. Differences in baseline characteristics will be accounted for by using covariance adjusted models.

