We will describe differences in baseline characteristics between participants with complete versus incomplete follow-up to assess any bias (e.g., age) in those who do not return for follow-up. However, according to ITT analyses, all participants including those that do not complete the intervention will be analyzed as part of the trial. Using hierarchical regression models, we will be able to explore whether changes in any cognitive or neuroimaging metric (e.g., white matter integrity) varies as a function of improvements in PA or fitness independently of assigned group. We also appreciate that there will be significant individual variability in factors such as body mass, blood pressure, fitness level, or SES. Instead of modeling this variation as ‘noise’ we plan to take advantage of the variability to further explore, independently of group assignment, the associations between cognitive and brain imaging metrics and initial levels and individual change trajectories. Main effects and interaction terms will be modeled in these regression analyses and time-dependent changes will be explored and illustrated by scatter plots. These analyses will be useful for generating future hypotheses and questions.

Power Analyses: Our proposed sample size of 180, with randomization of 90 participants in each group, is based on effect sizes from preliminary data. Even when accounting for attrition and retention of ~70% of participants (65 in each group), we are sufficiently powered to detect effects in cognitive and brain outcomes and to test for mediation.

Cognitive performance: Our prior PA interventions have found moderate sized effects on cognitive function after 6-months with a Cohen’s d ranging from 0.40 to 0.80 depending on the outcome. In our analysis of the pilot data from the African Dance intervention with only 19 participants (9 in the Dance group) we estimate similar or greater effect sizes of ~.70. If we estimate an effect of 0.70, 65 participants per group after attrition will provide us with >91% power to examine our primary hypotheses.

Brain volumetrics: Our prior 6-12 month PA interventions have used between 30 and

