60 subjects per group with Cohen's d ranging between 0.40 and 0.50 using similar analysis approaches. Cross-sectional research has reported significant effects of PA on brain volume with only 32 subjects and effect sizes between 0.50 – 0.60. Preliminary data on 37 African Americans from one of our prior studies suggest that cross-sectional differences between African Americans engaging in PA compared to those not engaging in PA are larger than for whites (Cohen's d = 1.83). These studies argue for a moderate-to-large effect of PA on brain volume depending on the sample, the measure of PA and fitness, and the brain metric used. If we estimate a conservative effect size of 0.50, 65 participants per group will be sufficient to detect differences in brain volume at 81% power.

Diffusion tensor imaging: Changes in white matter have been detected in PA interventions in as little as 6-months with only 50 subjects. In a 12-month PA intervention, we found increased FA with only 35 subjects in each group with an estimated effect size of 0.70. Based on an estimated effect size of 0.75, we should have >85% power with 65 participants per group to test our main hypotheses as well as enough power for exploratory analyses.

Task-evoked activity: Task-evoked brain imaging studies of PA have found statistically significant effects with 30 - 50 subjects per group with effect sizes ranging between 1.0 and 1.3 depending on the region examined and the task employed. Cross-sectional studies of fitness on brain activity report even larger effects up to 1.70. These patterns indicate a large effect size of PA on brain function, so 65 participants per group will provide us with substantial power to test our main aims and hypotheses.

Connectivity: With only 65 people, we have shown that a PA intervention is effective at enhancing functional connectivity in prefrontal-inhibitory networks. The difference between the groups for prefrontal cortex connectivity was .15 with a standard deviation of .10 suggesting an effect size of 1.5 (Cohen's d). Therefore, similar to the effect sizes and power for the other measures, 65 participants per group should be sufficient for detecting changes as a function of the intervention with >85% power.

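### The 81% power for brain volume is an uncorrected single-test figure at the superseded target of 180; at 150 it is about 71–73% uncorrected and 61–72% once two primary outcomes are corrected for

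*Combined protocol and SAP*

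**What the plan says.** The brain volumetrics paragraph appears in protocol section 1.3.4 and again in the SAP. It begins "If we estimate a conservative effect size of 0.50" and concludes that "65 participants per group will be sufficient to detect differences in brain volume at 81% power". The cognitive paragraph (section 1.3.3 and the SAP) takes an effect of 0.70 and says that "65 participants per group after attrition will provide us with >91% power to examine our primary hypotheses". Both rest on 90 randomised per arm with about 70% retained, given as 65 per arm.

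On testing, section 1.3.1 and the SAP say "All analyses will be two-tailed" and, for group differences on all cognitive and imaging measures, that "multiple comparisons will be corrected by standard protocols". No alpha, correction method or family is given, and no power paragraph mentions a correction.

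The primary outcomes are named only in section 1.11, in the definition of loss to follow-up: "primary outcomes (executive functioning and hippocampal volume". The SAP names none. Section 1.7.3 lists four tests under executive function: Trail Making B, Dimensional Card Sort, Flanker and Color-Word Stroop. It defines no composite and no lead test.

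The closing paragraph of the SAP lowers the target from 180 to 150 and says that power remains sufficient, without a figure.

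**The concern.** A power figure should describe the test that will be run, at the sample size that will be available. The 81% appears to do neither: it takes no account of the promised correction, and it uses a number per arm that the reduced target will not supply at the planned retention.

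Two things are at stake. The sponsor and monitoring board may believe that the hippocampal question has a better chance of a clear answer than it has. Also, while the executive score, the family and the method are all unstated, they can still be chosen after the data are seen, which leaves the type I error of the confirmatory claim uncontrolled.

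**Working it through.** **Inputs from the documents.** Effect 0.50 for volume (section 1.3.4, SAP). Effect 0.70 for cognition, within a stated range of 0.40 to 0.80 (section 1.3.3, SAP). 65 analysed per arm from 90. Two-sided tests. Equal allocation (section 1.9). Current target 150 (end of SAP).

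**Assumed.** Alpha 0.05, because none is printed. The 0.70 is taken to apply to a single executive score. The comparison is a two-sample t test, which is what reproduces the plan's figure.

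**Formula.** Noncentrality δ = d√(n/2), with 2n − 2 degrees of freedom. Power is the probability that a noncentral t exceeds the two-sided critical value in absolute size.

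**1. The plan's figure.** δ = 0.50 × √32.5 = 2.850 and the critical value is 1.979, giving 80.8%. The normal approximation is Φ(2.850 − 1.960) = 81.3%. At 0.025 the critical value is 2.268 and power is 71.9%. So 81% is one test at uncorrected 0.05.

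**2. Analysed number at the current target.** 150/2 = 75 per arm. At 70% retention, 75 × 0.70 = 52.5, taken as 52. At the plan's own ratio, 75 × 65/90 = 54.2, taken as 54. Keeping 65 per arm would need 65/75 = 87% retention.

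**3. Single-test power.**

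| Analysed per arm | Volume (0.50) at 0.05 | Volume at 0.025 | Executive (0.70) at 0.05 | Executive at 0.025 |
|---|---|---|---|---|
| 65 | 80.8% | 71.9% | 97.7% | 95.6% |
| 54 | 73.1% | 62.8% | 95.0% | 91.2% |
| 52 | 71.4% | 60.9% | 94.2% | 90.0% |

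The 0.025 columns are the Bonferroni power for two primaries, and also the first Holm step.

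**4. Holm over two primaries.** Volume is significant if its p-value is at most 0.025, or if it lies between 0.025 and 0.05 and executive function has p ≤ 0.025. With independent tests:

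Holm power = P_V(0.025) + [P_V(0.05) − P_V(0.025)] × P_E(0.025)

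- 65 per arm, executive 0.70: 71.9 + 8.9 × 0.956 = 80.4%
- 54 per arm, executive 0.70: 62.8 + 10.3 × 0.912 = 72.2%
- 52 per arm, executive 0.70: 60.9 + 10.5 × 0.900 = 70.4%

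For an executive effect of 0.40, P_E(0.025) is 50.7%, 42.6% and 41.0% at 65, 54 and 52 per arm, giving 76.4%, 67.1% and 65.2%. For no executive effect it is 2.5%, giving about 72%, 63% and 61%. Simulation with a correlation of up to 0.5 between the two tests moved these volume figures by no more than about 1.3 points.

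By the same formula with the roles exchanged, executive power under Holm is 90.0 + 4.2 × 0.609 = 92.6% at 52 per arm and 91.2 + 3.8 × 0.628 = 93.6% at 54. An assumed correlation of 0.2 lowers these to 92.2% and 93.2%, so about 92–93%.

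**5. If the four executive tests are counted separately (five tests).** Bonferroni at 0.01 gives volume power of 59.4% at 65 per arm, 49.3% at 54 and 47.3% at 52. Simulated Holm with all four executive effects at 0.70 gives about 79–80% at 65 per arm and 67–69% at 52–54.

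**The case against.** The strongest reply is that the arithmetic is right and the correction method is open. A reader might infer that the promised correction by itself makes 81% unattainable. The documents do not support that: they name no method, and at 65 per arm Holm with the plan's own executive effect leaves about 80%. This stands, with a limit. The protection depends on an executive effect of 0.70, which the plan draws from 19 pilot participants, and it shrinks at the low end of the plan's own range.

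A reader might also infer that the power figures use different alphas, because 91% at an effect of 0.70 is close to what alpha 0.01 gives (91.4%). But the plan states more than 91%, which is a floor, and alpha 0.05 satisfies it at 97.7%. No second alpha is shown.

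Nor should the family-wise error be read as 22.6%. That is 1 − 0.95⁵, for five independent and uncorrected tests. Four tests of one domain in the same people are likely to be correlated, and the plan promises a correction. It is an upper-end illustration only; for two independent uncorrected tests it is 1 − 0.95² = 9.75%.

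Last, adjustment for baseline could recover power if the 0.50 is in follow-up standard deviation units. To match 65 per arm uncorrected, the baseline to follow-up correlation would have to be √(1 − 52/65) = 0.45 at 52 per arm, or √(1 − 54/65) = 0.41 at 54. The documents do not define the scale of the effect, give no correlation and claim no such gain, so this cannot be credited to the stated figure.

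**Conclusion.** The point holds as a fault of specification and of an outdated figure, not as an arithmetic error. The 81% describes one uncorrected test at a sample size that the plan no longer targets. Most of the shortfall comes from the cut to 150: uncorrected power falls from 80.8% to 71–73%. Correction over two primaries then takes between about 1 point (Holm, executive effect 0.70) and 10 points (Bonferroni, or Holm with no executive effect), giving 70–72% down to 61–63%. The plan's silence on method and family leaves that whole range open.

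These values assume alpha 0.05, retention of 70% to 72%, an effect of 0.50 on the scale that reproduces the plan's figure, and no gain from baseline adjustment. The stated cognitive power is much less affected: about 92–93% under Holm at the current target if the effect is 0.70, with a first-step floor of 90–91%.

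**What to change.** In the SAP:

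1. State a family-wise two-sided alpha of 0.05.
2. Name two primary outcomes: one executive-function score, fixed before unblinding (for example, a composite of the four listed tests), and hippocampal volume. Test the pair by Holm and label every other test, domain and region as secondary. Holm is one reasonable choice; what matters is that the method and family are fixed in advance.
3. Replace both power figures with values at the current sample size. For volume (0.50): about 70–72% under Holm if the executive effect is 0.70, with a floor of 61–63%. For executive function (0.70): about 92–93% under Holm, with a first-step floor of 90–91%. State the retention used, and the effect scale and any baseline correlation if a gain from adjustment is claimed.

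The cost is SAP wording and a less favourable stated power for volume. No new participants or data are needed.

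### The 81% power for brain volume is an uncorrected two-sided 0.05 figure, although the plan promises a multiplicity correction, names no alpha, family or procedure, and has since cut the target to 150

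*Combined protocol and SAP*

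**What the plan says.** The power text appears twice with the same figures, in protocol 1.3.2-1.3.4 and in the Statistical Analysis Plan under Power Analyses, Cognitive performance and Brain volumetrics.

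- **Sample size.** 180 randomised, 90 per group, with about 70% retained, given as 65 per group.
- **Cognition.** "If we estimate an effect of 0.70, 65 participants per group after attrition will provide us with >91% power".
- **Brain volume.** "If we estimate a conservative effect size of 0.50", then "65 participants per group will be sufficient to detect differences in brain volume at 81% power".
- **Error rate.** "All analyses will be two-tailed" (protocol 1.3.1 and the SAP's opening paragraph). No significance level is given in either document.
- **Multiplicity.** For the group contrasts on the cognitive and neuroimaging outcomes, "multiple comparisons will be corrected by standard protocols". The method, the family and any testing order are left open.
- **Primary outcomes.** Protocol 1.11, in defining loss to follow-up, refers to "missing data that is contributing to the primary outcomes (executive functioning and hippocampal volume".
- **Current target.** The closing section of the SAP lowers the target from 180 to 150 and says power remains sufficient, without a figure.

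**The concern.** A power figure is informative only for the test that will be run. Here one of two primary outcomes carries a point value of 81%, with no mention of a correction, while the analysis section says a correction will be applied. Unless the correction leaves the brain-volume test at the full 0.05, the stated power is too high.

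The omission also leaves the decision threshold open. A hippocampal p-value of 0.03 would be positive at 0.05 and negative at 0.025, and nothing in the plan settles which applies. Fixing that before the results are seen is a basic purpose of an analysis plan. The claim of sufficient power at 150 cannot be checked until it is settled.

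**Working it through.** **Inputs.** d = 0.50 (brain volume), d = 0.70 (cognition), cognitive range 0.40 to 0.80 and n = 65 per group, all from the power sections; two-sided tests. Alpha is not stated, so 0.05 is tried first. The figures treat d as the standardised group difference in the analysed contrast.

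**Formula.** Two-sample t-test, equal groups: noncentrality = d × √(n/2), df = 2n − 2, power = P(T > t(1 − α/2, df)) under the noncentral t.

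**Step 1: reproduce the 81%.** Noncentrality = 0.50 × √32.5 = 2.85; df = 128; critical value at 0.05 = 1.979. Power = **80.8%** (81.3% by the normal approximation). Solving backwards from 81% gives alpha 0.051 (t) or 0.049 (normal). The figure is an unadjusted two-sided 0.05 calculation.

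**Step 2: check the cognitive figure.** Noncentrality = 0.70 × √32.5 = 3.99. Power is **97.7%** at 0.05 and **95.6%** at 0.025. Both satisfy the stated bound of more than 91%.

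**Step 3: brain volume under a correction over the two named primaries, 65 per group.**

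- *Bonferroni.* Alpha 0.05/2 = 0.025, critical value 2.268: power **71.9%**.
- *Holm.* Brain volume is significant if p < 0.025, or if p < 0.05 and cognition has p < 0.025. With independent outcomes, power = P(0.025) + [P(0.05) − P(0.025)] × P_cog(0.025).
  - Cognition d = 0.70: 0.7194 + (0.8076 − 0.7194) × 0.9564 = **80.4%**. By simulation with the normal approximation and correlations of 0 to 0.6, it is about 81%.
  - Cognition d = 0.40: 0.7194 + (0.8076 − 0.7194) × 0.5066 = **76.4%**.
- *A wider family* costs more under Bonferroni: over three tests (0.05/3), power is 66.4%.

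**Step 4: the current target of 150.** Equal allocation gives 75 per group (assumed). Retention of 70% leaves 75 × 0.70 = 52.5; the plan's own ratio of 65/90 = 72.2% leaves 54.2. So 52 to 54 per group are used.

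| Outcome | Procedure | Power at 52-54 per group |
|---|---|---|
| Brain volume, d = 0.50 | Unadjusted 0.05 | 71.4-73.1% |
| Brain volume, d = 0.50 | Alpha 0.025 | 60.9-62.8% |
| Cognition, d = 0.70 | Unadjusted 0.05 | 94.2-95.0% |
| Cognition, d = 0.70 | Alpha 0.025 | 90.0-91.2% |

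Holm at 53 per group with cognition at d = 0.70 and independent outcomes: 0.6184 + (0.7224 − 0.6184) × 0.9063 = **71.3%** for brain volume.

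**The case against.** **The arithmetic is not wrong.** The 81% reproduces and the bound for cognition is true. That stands. The point is that the 81% is not tied to the corrected analysis the plan promises.

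**A correction need not cost power.** The plan names no Bonferroni split. Holm over exactly two tests keeps about 80%, and Hochberg about 81% by the normal approximation, at the plan's own effect sizes. This stands too, so it would be wrong to say that the 81% exists only without a correction. But the rescue needs three things the plan does not state: a procedure of that kind, a family limited to these two outcomes, and a cognitive effect near 0.70. The correction sentence itself covers all cognitive and neuroimaging outcomes.

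**A reader might infer that the two power figures rest on different alphas.** At alpha 0.01, d = 0.70 with 65 per group gives 91.4%, close to the cognitive figure. The documents do not support that inference. The figure is a lower bound, and 0.05 satisfies it. The plan's other bounds are equally loose: for diffusion imaging (d = 0.75, more than 85%), 0.05 gives 98.9%, and reading 85% as exact would point to an alpha of about 0.0012 to 0.0016. The value 0.01 appears nowhere in the plan.

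**The family is partly inferred.** The two primaries are named only in the definition of loss to follow-up, and the 81% is given for brain volume in general. This is fair, and it is a reason to write the family down.

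**The meaning of d is open.** The planned analysis is a mixed model with baseline and 6-month values. If d is in raw outcome units and the contrast is adjusted for baseline, power at 0.025 and 65 per group would be about 76% with an assumed baseline/follow-up correlation of 0.3, and about 85% with 0.5. The documents give neither a definition of d nor a correlation, so 72% is not a fixed replacement value.

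**Conclusion.** The concern holds in a limited form. The stated 81% takes no account of a correction the plan says it will make, and the plan does not specify that correction well enough to say what the power is. At 65 per group the overstatement runs from almost nothing (Holm, cognition at d = 0.70) through about 5 points (Holm, cognition at d = 0.40) to about 9 points (Bonferroni over two). A wider family would generally add to it.

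The cut to 150 matters at least as much: at 52-54 retained per group, brain-volume power is about 8 to 10 points below 81% before any correction. Cognition stays at 90% or more in every case computed at d = 0.70.

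These results assume equal allocation, 70-72% retention, d as the standardised difference in the analysed contrast and, for the Holm formula, independent outcomes. They do not show that the two primaries were powered at different alphas.

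**What to change.** In the SAP, and to match in protocol 1.3.1, 1.3.3, 1.3.4 and 1.11:

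1. State a two-sided family-wise alpha of 0.05 for executive function and hippocampal volume.
2. Name the procedure, for example Holm over these two outcomes, and say how the remaining cognitive and imaging outcomes are handled.
3. Say what d standardises (raw outcome, change, or baseline-adjusted contrast) and, if a baseline/follow-up correlation is used, give it.
4. Replace both power figures with values under that procedure at the target of 150, with the retained number per group stated. On the assumptions above, Holm gives brain volume about 71% at 53 per group if cognition has d = 0.70. The value at 0.025 is about 61-63% for brain volume and 90-91% for cognition.

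This is wording only: no change to conduct or data collection. The cost is a less favourable stated power for brain volume.
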